- If during the course of treatment, a subject experiences a new onset cardiovascular adverse event consistent with Common Terminology Criteria for Adverse Events (CTCAE) Version 5.0 of Grade ≥ 2 , such subjects should be discontinued from further dosing and, if applicable, followed for resolution.
- If a subject experiences a new onset adverse hematologic adverse event (including laboratory abnormalities) of Grade ≥ 2 , such subjects should first have laboratory abnormalities verified by repeat measure, and if repeat measure confirms the new onset abnormality, such subjects should be discontinued from further dosing, and if applicable, followed for resolution.
- If a subject experiences an adverse event Grade ≥ 3 for any organ system, such subjects should be discontinued from further dosing and, if applicable, followed for resolution.
- The study drug should be discontinued in subjects who develop evidence of hepatocellular injury that may be caused by the study drug consistent with Hy's Law. Such an adverse event should be reported as a serious adverse event (SAE).

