7.2.3 Possible Case of Drug-Induced Liver Injury (DILI)

Subjects who present with evidence of hepatocellular injury that may be caused by drug ingestion consistent with Hy's Law with all of the following criteria acutely should be re-evaluated:

- ALT or aspartate aminotransferase (AST) > 3× ULN
- Total bilirubin > 2× ULN
- No signs of cholestasis (alkaline phosphatase [ALP] < 2× ULN)
- No other assignable cause such as liver metastases, pre-existing hepatic disease, viral hepatitis, alcohol abuse, ischemia, etc.

Re-evaluation should include repeat of AST, ALT, total bilirubin and alkaline phosphatase along with additional laboratory assessments including: albumin, creatine kinase, direct bilirubin, gamma-glutamyl transferase (GGT), and prothrombin time (PT)/international normalize ratio (INR). Additional medical and/or laboratory investigation to investigate other potential causes (e.g., alcohol use, infectious hepatitis) should also be considered and assessed as appropriate by the Investigator. Potential cases satisfying Hy's law should be reported as SAEs. If a subject satisfies Hy's law, study drug should be discontinued for the subject.

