### C. Adverse Events of Clinical Interest

A separate analysis focused on adverse events of clinical interest will also be performed. Adverse events of clinical interest are as follows and identified by the eCRF page "Adverse Events":

- Malignancy
- Major adverse cardiac events (MACE)
- Tuberculosis (TB)
- Inflammatory bowel disease (IBD)
- Depression and suicidal ideation and behavior
- Serious or opportunistic infection
- Hypersensitivity reactions

The counts and percentages will be summarized for each PT and SOC by treatment group and overall. Additional summaries will also be provided by strongest relationship to study drug and worst severity.

The time to first TEAE of clinical interest during the week 16 treatment period will be assessed by Kaplan-Meier estimates (K-M plot) by each AECI category. The time is defined as the date of first event – the date of first dose + 1. Subjects without an event will be censored at the last AE assessment date within the 16 week of treatment period.. Graphs of cumulative incidence rate over time will be presented by treatment group.

The adverse events of clinical interest will be present in a separate listing.

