### D. Clinical Laboratory Test

All laboratory measurements include hematology, clinical chemistry, and urinalysis results, and will be converted to standard international (SI) units and US conventional units. Laboratory data will be summarized using descriptive statistics for the observed and change from baseline by treatment arm and overall. Worst post-baseline CTCAE grade shift from baseline tables will also be provided for hematology, clinical chemistry and urinalysis for lab test with available grading. Shift tables will be used to present the number and percentages of subjects with laboratory values within/outside normal reference ranges for parameters that do not have a CTCAE grading. Clinically significant changes will be reported as AE.

All laboratory data, including serology, pregnancy and other lab test, will be present in the listings. A by-subjects listing will also be provided for subjects with abnormal laboratory results.

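### The SAP plans no laboratory-based count by arm of subjects meeting the protocol's combined liver-injury criterion, and the protocol states that criterion in two different ways

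*SAP*

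**What the plan says.** **Protocol.** Section 7.2.1 states: "The study drug should be discontinued in subjects who develop evidence of hepatocellular injury that may be caused by the study drug", refers to Hy's Law, and requires an SAE report. Section 7.2.3 gives the pattern: "ALT or aspartate aminotransferase (AST) > 3× ULN", "Total bilirubin > 2× ULN", ALP below 2 times ULN, and a causal condition, "No other assignable cause such as liver metastases, pre-existing hepatic disease, viral hepatitis, alcohol abuse, ischemia, etc". It asks for repeat liver tests when the pattern appears. Appendix 11 (note a to Table 7) sets a second combined rule for SAE reporting, with different limits and no causal condition. The tests needed for 7.2.3 are all in the chemistry panel, and the schedule of activities runs laboratory tests to Day 169.

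**SAP laboratory plan (VII.D).** Observed values and changes from baseline are summarised by arm. For categories: "Worst post-baseline CTCAE grade shift from baseline tables will also be provided for hematology, clinical chemistry and urinalysis for lab test with available grading". Tests without a CTCAE grade get normal-range shift tables. All laboratory data are listed, and subjects with abnormal results have their own listing.

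**SAP adverse events (VII.B and VII.C).** Serious TEAEs and TEAEs leading to study drug withdrawal are tabulated by SOC and preferred term for each treatment group. A TEAE must start between first dose and 30 days after end of treatment. Of the events of clinical interest the SAP says: "Adverse events of clinical interest are as follows and identified by the eCRF page". Seven categories follow, none hepatic.

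**The concern.** The pattern the protocol acts on is a joint one: transaminase and bilirubin raised in the same subject. A table for each test shows how many subjects had each rise, not how many had both. Isolated ALT rises in some subjects and isolated bilirubin rises in others look the same in such tables as combined rises in the same subjects, yet only the combined pattern triggers the Hy's Law rule.

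At stake is whether the study report can compare this harm between doses and placebo without relying on AE reporting and coding. TEAE incidence is a co-listed primary endpoint. Earlier dosing in AD subjects lasted 28 days against 16 weeks here, there is no independent data monitoring committee, and the results are meant to inform pivotal studies.

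**Working it through.** **1. Is any combined laboratory output planned?** I read SAP section VII from exposure to the COVID-19 assessment. No derivation, table or figure combines liver tests within a subject. The SAP does plan threshold counts elsewhere: VII.I counts QTcF above 450, 480 and 500 ms and increases above 30 and 60 ms. The liver rule also has numerical limits in the protocol but no equivalent table.

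Whether any CTCAE grade boundary coincides with 3 or 2 times ULN cannot be checked from the documents. It does not matter here, because a per-test table would still not give the joint count.

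**2. Can per-test tables give the joint count?** The denominator is the planned arm size: 60 / (1 − 0.10) = 66.7, rounded up to 67, and 4 × 67 = 268, as the SAP states. If *a* subjects meet the transaminase limb and *b* the bilirubin limb among *n*, the number meeting both lies between max(0, *a* + *b* − *n*) and min(*a*, *b*). With *n* = 67 and assumed counts:

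| *a* | *b* | Possible joint count |
|---|---|---|
| 1 | 1 | 0 to 1 |
| 3 | 2 | 0 to 2 |
| 3 | 3 | 0 to 3 (3/67 = 4.5%) |
| 5 | 3 | 0 to 3 |

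The margins settle the answer only when one of them is zero.

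**3. What would a count of zero support?** The exact one-sided 95% upper bound for zero events is 1 − 0.05^(1/n):
- One arm, n = 67: 4.37%.
- Three RPT193 arms pooled, n = 3 × 67 = 201: 1.48%.

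The chance of seeing at least one case is 1 − (1 − p)^n. At assumed true rates of 0.1%, 0.5% and 1% this is 6.5%, 28.5% and 49.0% in one arm, and 18.2%, 63.5% and 86.7% pooled (same rate at each dose). A pooled column is therefore worth having.

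**4. How complete is the AE route?** A case handled as the protocol requires enters the by-arm table of serious TEAEs and, if dosing is stopped for it, the table of TEAEs leading to withdrawal. Four limits remain:
- It depends on the case being recognised and reported.
- Counts are by preferred term. Cases may spread over several terms, and no row identifies the combined pattern.
- Dosing runs through Day 112, so the TEAE window closes at about Day 142 (112 + 30). An onset first found at Day 169 falls outside every TEAE table and would show only in listings and the overall any-AE row.
- SAP VII applies the efficacy windows to safety analyses that need windows. SAP IV.C sets unscheduled visits aside when an in-window scheduled one exists. VII.D does not say whether the repeat tests required by 7.2.3 count toward the worst post-baseline value.

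**5. The two protocol criteria side by side.**

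| Element | Section 7.2.3 | Appendix 11, note a |
|---|---|---|
| Transaminase | ALT or AST, > 3 × ULN | ALT only, ≥ 3 × ULN |
| Bilirubin | Total > 2 × ULN | ≥ 2 × ULN, with > 35% direct |
| ALP | < 2 × ULN | Not mentioned |
| Alternative limb | None | ALT ≥ 3 × ULN with INR > 1.5, if measured |
| Other cause | Must be absent | No such condition |

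An AST-only rise, or bilirubin without the direct fraction, can meet the first but not the second. A subject with an assigned cause, or with ALP at or above 2 × ULN, can meet the second but not the first. Appendix 11 also points to Section 7.1 for liver stopping criteria, whereas the protocol's liver rules stand in 7.2.

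**The case against.** The strongest reply is that these cases are already captured. A reader might infer from VII.D that combined cases are never counted by arm. The documents do not support that: VII.B tabulates serious TEAEs and TEAEs leading to withdrawal by treatment group, and the protocol sends Hy's Law cases down both routes.

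A reader might also infer from 7.2.3 that a case becomes an SAE only when the investigator finds no other cause. Appendix 11 contradicts this, since its SAE rule rests on laboratory values alone. Many cases with an assigned cause would therefore still be reported.

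Listings are ordered by treatment, subject and time (SAP IV.J), so concurrent rises in one subject can be found and counted by hand. Finally, the documents report no liver signal: no adverse effects in dogs up to 16 weeks, minimal biochemistry changes in Phase 1, and raised ALT (> 2.5 × ULN) excluded at entry.

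All of this stands and narrows the point. What survives is that no planned output gives the combined count from the laboratory data. The AE route can miss AST-only rises and bilirubin below the Appendix 11 direct fraction when a cause has been assigned, as well as late onsets and unreported cases. A hand count from listings made after unblinding would have no prespecified definition.

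**Conclusion.** The point holds in a limited form. The SAP plans no laboratory-based count by arm of subjects meeting the combined liver-injury criterion, and its per-test tables cannot supply one. Cases reach by-arm tables only through AE reporting, under coded terms and inside the TEAE window. The two protocol criteria differ and must be reconciled before any combined count can be programmed; which is clinically right is for the sponsor to settle.

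No trial figure changes. The 3-and-3 example, the zero-event bounds (4.4% for 67 subjects, 1.5% for 201) and the detection probabilities are illustrations. They assume the planned arm sizes and, for the probabilities, chosen event rates, because the documents give no liver event rate for RPT193. This is a worthwhile, inexpensive improvement to safety reporting. It does not bear on the validity of the efficacy analysis.

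**What to change.** First, the sponsor reconciles Protocol 7.2.3 and Appendix 11, including the cross-reference to Section 7.1.

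Then SAP VII.D is extended before unblinding. SAP I.B allows changes until then, and IV.F lets a limited sponsor group see unblinded results at the Week 16 efficacy analysis, so the change should precede that analysis. Add:

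- **Table**, Safety Analysis Set, by arm and for all RPT193 arms pooled. Count subjects meeting each laboratory component and the reconciled combined laboratory criterion, regardless of assigned cause. Use all post-baseline values, including unscheduled and ET/Discon visits, and state whether the elevations must be concurrent (7.2.3 refers to an acute presentation but sets no interval).
- **Figure**: peak ALT (or AST) as a multiple of ULN against peak total bilirubin as a multiple of ULN, by arm.
- **Listing** of subjects meeting the laboratory criterion, showing whether an SAE was filed.

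The cost is the SAP wording and the programming of one table, one figure and one listing from data already collected. No new samples or visits are needed.

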## **E. Vital Signs**

Vital sign tests will include sitting systolic and diastolic blood pressure (mmHg), pulse rate (beats/minute), respiratory rate (breaths/minute), body temperature (C), weight (kg), height (cm), and body mass index (BMI) (kg/m^2). Vital sign parameters will be summarized using descriptive statistics at each assessment timepoint by treatment arm and overall. Change from Baseline will also be summarized descriptively by treatment arm and overall. Clinically significant changes will be reported as AE.

All vital sign data will be displayed in a by-subject listing.

## **F. Physical Examination**

Physical examinations will consist of general appearance, skin, eyes/ ears/ nose/ throat, head/ neck, cardiovascular, respiratory, gastrointestinal, abdomen, extremities, lymph nodes, musculoskeletal, neurologic function and other. Abnormal physical examination findings may be reported as an adverse event.

The findings will be summarized by counts and percentages at each assessment timepoint by treatment group and overall. All data will be provided in a data listing. Abnormal physical examination findings will also be presented in a by-subject listing.

## **G. Prior and Concomitant Medications**

Prior medications are defined as any medication that stopped before the date of the first dose of study drug. These medications will be recorded on both the "Prior Dupilumab and/or Tralokinumab Meds" and the "Prior and Concomitant Medications" eCRF form. Concomitant medications are defined as any medication that was ongoing or ended at the date of first dose, or any medication that started on or after the date of first dose. These medications will be recorded on the "Prior and Concomitant Medications" eCRF form.

All medications will be coded using the World Health Organization Drug Dictionary (WHO-DD) version B3 Global September 2021. Prior and concomitant medications will be summarized separately by Anatomical-Therapeutic-Chemical (ATC) level 4 classification and PT by treatment group and overall.

Medications that are indicated as rescue medications will also be summarized. Detailed information of rescue medications/procedures including duration of use and incidence of use will be summarized by topical and systemic groups. Kaplan-Meier (K-M) curves for time to first rescue use will be generated. The duration of use will be calculated based on the first start date and end date by topical and systemic groups. Missing dates will be imputed following Section IV.D.

All medications will be presented in a listing. A separate listing will be presented to include the rescue medications.

## **H. Concurrent Procedure**

All concurrent procedures will be coded according to MedDRA version 24.1. Concurrent

procedures will be summarized by SOC and PT by treatment group and overall.

All concurrent procedures will be presented in a listing.

## I. ECG

12-lead electrocardiogram (ECG) in triplicate are performed at the visits designated in the SOA.

ECG measurements include mean heart rate (msec), PR interval (msec), RR interval (msec), QRS interval (msec), QT uncorrected (msec), QT corrected with Bazzett's formula (msec) and QT corrected with Fridericia formula (msec). The average of the triplicate assessments will be used for summary purposes. The actual value and change from baseline will be summarized using descriptive statistics at each assessment visit by treatment group and overall.

Absolute QTcF interval prolongation will be summarized by counts and percentages across all post-baseline assessments using the following criteria:

- QTcF interval >450 ms
- QTcF interval >480 ms
- QTcF interval >500 ms
- QTcF interval increases from baseline >30 ms
- QTcF interval increases from baseline >60 ms

The frequency count and percentage of the worst overall ECG evaluation among the triplicate will be summarized at each assessment visit by treatment group and overall. The best to worst overall assessment will be order as: normal, abnormal not clinically significant, abnormal clinically significant.

Clinically significant ECG abnormalities will be reported as AE.

All ECG data will be presented in listing.

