2.2.2.4 Clinical Pharmacokinetics and Pharmacodynamics

Clinical pharmacokinetics (PK) and pharmacodynamics data have been obtained from a Phase 1 study, RPT193-01, entitled: “A Phase 1, randomized, double-blind, placebo-controlled, single-dose escalation, multiple-dose escalation, and food effect study of RPT193 in healthy subjects and subjects with moderate-to-severe atopic dermatitis.”

In the Phase 1 trial of healthy subjects, RPT193 has demonstrated increases in exposure following increasing single doses (5 to 400 mg) and up to approximately 2-fold accumulation following multiple doses (50 to 400 mg once daily [QD] for 7 doses), and minimal to no food effect, with a mean plasma half-life of approximately 24 hours.

Following administration of multiple doses of 400 mg RPT193 QD for 28 days in subjects with AD in either a fasted or fed state, the median time to maximum concentration [t_{max}] of RPT193 on Day 28 was ~6 hours. There was a substantial increase in C_{max} and AUC on Day 28 when compared to Day 1. Overall, the data indicate similar PK parameters in both healthy volunteers and AD following multiple doses of 400 mg QD.

Please refer to the Investigator’s Brochure for a detailed description of the clinical PK and pharmacodynamics of RPT193.

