## VII. Safety Analyses

All safety analysis will be based on the safety analysis set. The safety analyses which need analysis window, eg. change from baseline, will follow the analysis window for efficacy data, unless it is specified in each section below.

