- f. FSH at Screening only for females of non-childbearing potential.
- g. The ACQ-5 instrument will only be assessed in subjects reporting a history of ongoing asthma at Screening.
- [REDACTED]
- i. Photographs will be taken at the selected sites. One or more most affected body regions, per Investigator's judgement, may be photographed.
- j. The e-Diary will be dispensed to the subject or the e-Diary application will be loaded to the subject's device at Baseline. Collection or removal of application will occur at EOS or at ET/Discon. Subjects enter e-Diary information on a daily basis for their compliance with study treatment starting Baseline/Day 1, recording daily pruritus, daily skin pain NRS, and ADSS starting at Baseline/Day 1.
- k. On Day 1, Day 15, Day 29, Day 57, and Day 85, the study drug will be administered at the study center after all other assessments are performed. All other daily drug intake will be self-administered by the subject, at home, at approximately the same time of the day through Day 112.
- l. PK blood sampling will be done pre-dose on Day 1, Day 15, Day 29 and Day 57.
- m. Tape stripping is only required for subjects in the US and Canada; tape stripping should not be performed for subjects in Poland. Tape strips will be collected from lesional and non-lesional skin pre-dose at Baseline. Tape strip samples will also be collected at the same sites sampled at Baseline on Day 29, Day 57, Day 113, and on Days 141 and 169, if applicable.
- n. Two skin microbiome samples will be collected at Baseline, one from lesional and one non-lesional skin. A skin microbiome sample will also be collected at subsequent visits at the same lesional site sampled at Baseline.
- o. Plasma blood sampling will be done pre-dose.
- p. The immunophenotyping sample is only required for subjects in the US and Canada; immunophenotyping samples should not be collected from subjects in Poland.
- q. Blood sample will be collected from subjects who have consented to participate in the genetic analysis component of the study. Participation is optional.

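### QTcF outlier counts and worst laboratory grades have no on-treatment limit, so they mix on-drug and off-drug values; an on-treatment split beside the all-post-baseline tables would be nearly free.

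*SAP*

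**What the plan says.** SAP VII.I (ECG) states: "Absolute QTcF interval prolongation will be summarized by counts and percentages across all post-baseline assessments using the following criteria". The criteria are QTcF above 450, 480 and 500 ms, and rises from baseline above 30 and 60 ms. SAP VII.D (Clinical Laboratory Test) states: "Worst post-baseline CTCAE grade shift from baseline tables will also be provided for hematology, clinical chemistry and urinalysis", for tests that have a grading. Neither section names a last day. The opening of SAP VII says that safety analyses needing windows "will follow the analysis window for efficacy data, unless it is specified in each section below", and those windows (SAP IV.C) run to Day 172.

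Other safety outputs in the same plan are limited. SAP VII.B counts an adverse event as treatment-emergent only if it starts within 30 days after the end of treatment. SAP VII.C limits time to first event of clinical interest to the 16-week treatment period.

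On dosing, SAP Appendix I footnote k says that doses not given at the clinic are "self-administered by the subject, at home, at approximately the same time of the day through Day 112". Protocol 2.2.2.4 reports a "mean plasma half-life of approximately 24 hours".

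**The concern.** A count of subjects who ever cross a threshold, or of the worst grade ever reached, can only grow as visits are added. Visits made well after the last dose add abnormalities at roughly the background rate in every arm, including placebo. If an effect exists only while the drug is on board, those visits contribute noise to the comparison and shrink the ratio between arms.

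The safety objective is the safety and tolerability of 16 weeks of once-daily dosing, so the natural question for these two tables is what happened on drug. As planned, they answer a wider question. They also differ from the adverse event tables: a laboratory value at Day 169 can set a completer's worst grade, yet an adverse event starting that day would not count as treatment-emergent.

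**Working it through.** The documents state no figure for QTcF or laboratory outliers, so there is nothing of the plan's own to reproduce.

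**Inputs**
- Last planned dose: Day 112 (SAP Appendix I, footnote k).
- Half-life: about 24 hours (Protocol 2.2.2.4, from healthy subjects; the same section describes similar PK in subjects with AD at 400 mg once daily).
- Post-baseline visits (SAP Appendix I): ECG and urinalysis on Days 29, 113 and 127; blood laboratory tests on Days 15, 29, 57, 85, 113, 127, 141 and 169. The ECG row in Protocol 1.3 cannot be aligned with its columns in the text available to me, so I rely on the SAP.
- Visit window: ±3 days from Day 29 on.
- Background rate per visit: not in the documents. Assumed range 0.5% to 10%, with an on-drug rate 2 or 3 times background.

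**Step 1. Time off drug for a completer.** Days off drug = visit day − 112. Share of drug remaining = 0.5^(days off drug).

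| Visit | Days off drug (range with window) | Share remaining at nominal day | Within 30 days of last dose? |
|---|---|---|---|
| Day 113 | 1 (−2 to 4) | 50% | yes |
| Day 127 | 15 (12 to 18) | 0.003% | yes |
| Day 141 | 29 (26 to 32) | effectively zero | nominally yes |
| Day 169 | 57 (54 to 60) | effectively zero | no |

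Off-drug looks are therefore 1 of 3 for ECG, 1 of 3 for urinalysis and 3 of 8 for blood tests.

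**Step 2. Effect on a worst-value count.** Let v be the background rate per visit. Count each subject once, treat visits as independent, and take k on-drug and m off-drug visits. On treatment, P = 1 − (1 − rate)^k in each arm. The off-drug visits add b = 1 − (1 − v)^m in both arms, so P(all) = 1 − (1 − P)(1 − b). The risk difference is multiplied by (1 − b), and the risk ratio moves toward 1.

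**Step 3. Two worked cases, drug doubling the rate.**
- ECG, v = 5%. On treatment: 1 − 0.90² = 19.0% vs 1 − 0.95² = 9.75%; ratio 1.95, difference 9.25 points. All visits: 1 − 0.90² × 0.95 = 23.1% vs 1 − 0.95³ = 14.3%; ratio 1.62, difference 9.25 × 0.95 = 8.8 points.
- Blood laboratory, v = 2%. On treatment: 1 − 0.96⁵ = 18.5% vs 1 − 0.98⁵ = 9.6%; ratio 1.92, difference 8.9 points. All visits: 1 − 0.96⁵ × 0.98³ = 23.3% vs 1 − 0.98⁸ = 14.9%; ratio 1.56, difference 8.3 points.

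**Step 4. Range over the assumed background rate** (on treatment → all visits).

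| v | ECG ratio, ×2 | ECG ratio, ×3 | ECG difference kept | Lab ratio, ×2 | Lab ratio, ×3 | Lab difference kept |
|---|---|---|---|---|---|---|
| 0.5% | 1.99 → 1.66 | 2.98 → 2.32 | 99.5% | 1.98 → 1.61 | 2.94 → 2.20 | 98.5% |
| 2% | 1.98 → 1.65 | 2.94 → 2.28 | 98.0% | 1.92 → 1.56 | 2.77 → 2.07 | 94.1% |
| 5% | 1.95 → 1.62 | 2.85 → 2.20 | 95.0% | 1.81 → 1.47 | 2.46 → 1.84 | 85.7% |
| 10% | 1.89 → 1.56 | 2.68 → 2.06 | 90.0% | 1.64 → 1.34 | 2.03 → 1.54 | 72.9% |

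**Step 5. Correlated visits.** A normal threshold model with within-subject correlation 0.5, v = 2% and a threefold on-drug rate gives ECG 2.84 → 2.22 (difference 6.7 → 6.3 points) and laboratory 2.58 → 2.01 (11.9 → 10.5 points). The direction is the same. The absolute difference shrinks somewhat more than under independence.

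**The case against.** Including follow-up values is a defensible safety choice. The documents themselves raise clinical effects that continue after dosing (SAP I.A, Protocol 2.2.2.6), and Protocol 8.2.4 follows significant laboratory abnormalities for 30 days after the last dose. A short plasma half-life does not exclude a delayed effect, so one cannot say that follow-up visits are uninformative about the drug. This stands, and it is why the all-visit table should stay.

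The outputs are also descriptive; no test or ratio against placebo is planned for them. A reader might infer that the tables conceal when an outlier occurred. The documents do not support that. SAP VII.I gives QTcF values, changes and the worst overall ECG evaluation by visit and arm, and all ECG and laboratory data are listed. What is missing is narrower: threshold counts and worst grades by period.

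A reader might also apply the 15-to-57-day range to ECG. On the SAP schedule only Day 127 is an off-drug ECG, and the same holds for urinalysis. Day 127 also serves as the early-termination visit, so for a subject who stops early it may fall close to the last dose and is not automatically off drug.

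Differential dropout is not an argument for the split. Early leavers miss on-treatment visits too, so an on-treatment count depends on retention as well.

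Finally, VII.I does not say whether it counts subjects or assessments; the working assumes subjects. Counted per assessment, a doubling over two of three ECGs would read (2 + 2 + 1)/(1 + 1 + 1) = 1.67 and the difference would fall by a third. The direction is unchanged.

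**Conclusion.** The point holds as a cheap improvement, not as an error. Neither summary has an on-treatment limit, and no planned table gives QTcF category counts or worst grades on drug separately from those off drug. For completers, one of three ECGs and three of eight blood draws are off drug.

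The cost falls mainly on the ratio. A true on-treatment ratio near 2 would read about 1.6 to 1.7 for QTcF and about 1.3 to 1.6 for blood tests over the assumed range. The absolute difference barely changes at low background rates; the material loss is in laboratory grades with a background near 10% per visit, where 73% of it is kept. All of this assumes an effect confined to the dosing period, one count per subject, full attendance and background rates that the documents do not give.

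A reader might go further and infer that the planned tables conflict with the plan's own adverse event limit throughout. They do not: nominally, Days 127 and 141 lie inside 30 days, so only the Day 169 blood draw falls clearly outside it.

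**What to change.** In SAP VII.D and VII.I, add two sets of columns to the worst-grade shift tables and the QTcF category table:
- **On treatment:** values from first dose up to a pre-specified short interval after each subject's own last dose, for example 7 days.
- **Follow-up:** all later values, with subjects having at least one such value as the denominator.

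Keep the all-post-baseline table, so that a delayed signal is not lost. State that each subject is counted once per category.

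Seven days is not taken from the documents. With visits inside their windows and a last dose on Day 112, Day 113 falls at most 4 days after the last dose and Day 127 at least 12, so any whole-day limit from 4 to 11 days sorts completers' visits identically. Tying the limit to actual last dose also places early-termination visits by their true timing, which visit labels would not.

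The cost is SAP wording and a few more table columns, with no new data. SAP I.B allows changes until unblinding. SAP IV.F provides for an unblinded efficacy analysis once all subjects have reached Week 16, so the change should be made before that.
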